## Costs to Subjects

Include a list of services and/or tests that will not be paid for by the sponsor and/or the study (e.g., MRI, HIV). Keep in mind that a subject will not know what is "standard" – and thus not covered by the sponsor/study – unless you tell them.

There are no reported costs to participants.

## Data and Safety Monitoring

The IRB requires review and approval of data and safety monitoring plans for greater than minimal risk research or NIH-funded/FDA-regulated clinical investigations.

- If you are conducting greater than minimal risk research, or your clinical investigation is NIH-funded, describe your Data and Safety Monitoring Plan (DSMP). [Click here for additional guidance on developing a Data and Safety Monitoring Plan](#).
- If this is a non-sponsored investigator-initiated protocol considered greater than minimal risk research, and if you are planning on using a Data and Safety Monitoring Board (DSMB) as part of your DSMP, [click here for additional guidance](#) for information to include with your IRB application.

i

Due to the vulnerable nature of the study population, the PI, will with input from Co-Investigators, be responsible for all data and safety. The principal investigator, with input from Co-Investigators, will be responsible for monitoring the data quality, and participant safety throughout this study, executing the DSMP and complying with the reporting requirements. The PI will also be responsible for providing a summary of the Data and Safety monitoring report on a semi-annual basis as a part of the progress report. The Data and Safety monitoring report will include the participants' socio-demographic characteristics, expected versus actual recruitment and retention rates, any relevant quality assurance or regulatory issues, summary of adverse events (AEs) and serious adverse events (SAEs), if any and any changes to the protocol as necessary.

Perinatal (maternal and neonatal / infant) data will be collected from the review of the electronic medical record system. Standardized data collection templates (REDCap) will be employed for data abstraction and management. Data will be de-identified and stripped of all identifying information prior to analysis. All data will be coded in a manner so that identifying data is not present on study materials. Each subject will have a unique identifier that will be linked to their name and medical record number in a file kept securely, and separately from other study data. All data will be kept in a secure place, with access restricted solely to study personnel authorized by the study PI. No patient will be identified individually in a manner that might reasonably subject the patient to identification in any publication or other presentation.

Monitoring for AEs will be based upon spontaneous self-report by the study participants and verification by medical and research staff. All AEs occurring during the study period will be documented and reported to the PI. The PI and Co-Investigators will follow all AEs to the point of satisfactory resolution, as outlined above. We do not anticipate any Serious Adverse Events (SAEs) (as defined by the FDA) with the interventions being proposed in the study. There are no invasive procedures being performed on pregnant women in the study.

[Back to Top](#)

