## 6 months Post-Partum

- 1) WHO QoL-BRF
- 2) Experience of Care and Health Outcomes (ECHO) - modified
- 3) Cornell Health Services Index (CHSI)
- 4) Fagerstrom nicotine Dependence
- 5) Edinburgh Depression Scale
- 6) GAD-7
- 7) Ages and Stages

Study participants will be asked to complete surveys in REDCap available on iPads dedicated specifically for this project; however, all participants will have the option to complete hard copies of the surveys if they prefer. Data from surveys completed on iPads will be uploaded directly into REDCap. Devices will be managed by UK Healthcare IT, which already deploys a large number of iPad devices and is very familiar with the security and management requirements of iOS based devices. UK Healthcare IT currently has a management app configured to ensure the security of the devices and to apply sufficient restrictions that the devices cannot be used for unintended purposes. All devices will be stored securely in locked cabinets.

We will be collecting the following maternal data:

1. Prenatal labs
2. Infectious complications
3. MAT program participation rate (by patient)
4. Study program participation rate (e.g. frequency of clinic attendance at telemedicine and/or group sessions);
5. Prenatal care attendance (medical record review).
6. Urine drug screen result on admission to labor and delivery, 3 and 6 months postpartum (obtained from medical records)
7. Smoking status: evaluated through patient interview and Fagerstrom Nicotine Dependence Scale at intake, 3rd trimester, 3 and 6 months postpartum.
8. Addiction severity: DSM-5 Criteria for Opioid Use Disorder at intake
9. Obstetric complications including but not limited to Preterm birth <37 GA, growth restriction (<10%ile), preterm rupture of membranes, preeclampsia, multiple gestation, gestational diabetes, chorioamnionitis, miscarriage, fetal demise, cesarean delivery (medical record review)
10. Overdose tracking (overdose reversal agent needed, admitted to hospital/ED for overdose): patient interview at every visit
11. Health services utilization: Cornell Health Service Index administered in 3rd trimester, 3 and 6 months post-partum
12. Patient experience of care: Experience of Care and Health Outcomes (modified) Survey administered in 3rd trimester, 3 and 6 months post-partum
13. Depression: Edinburgh Postpartum Depression Scale administered at intake, 3rd trimester, 3 and 6 months postpartum

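### Adverse-event detection rests on spontaneous self-report, and no rule carries the overdose, fetal-loss and infant data already collected into the semi-annual safety summary, which may miss serious events

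*Combined protocol and SAP*

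**What the plan says.** The Data and Safety Monitoring section gives one route by which an adverse event comes to notice: "Monitoring for AEs will be based upon spontaneous self-report by the study participants", with staff then verifying what is reported. It then sets a handling duty: "All AEs occurring during the study period will be documented and reported to the PI". On serious events it says: "We do not anticipate any Serious Adverse Events (SAEs) (as defined by the FDA) with the interventions being proposed in the study". The semi-annual report is to contain participant characteristics, recruitment and retention, quality or regulatory matters, and a "summary of adverse events (AEs) and serious adverse events (SAEs), if any and any changes to the protocol as necessary".

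The Data Collection & Research Materials section lists events that are collected actively. For mothers it has "Overdose tracking (overdose reversal agent needed, admitted to hospital/ED for overdose): patient interview at every visit". It also has a list of obstetric complications that ends "miscarriage, fetal demise, cesarean delivery (medical record review". For infants it lists NICU or nursery admission, other morbidities, length of stay and emergency visits. The stated sources are record review, interview, staff report, state Medicaid data and hospital discharge data.

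**The concern.** The protocol has two streams of information on serious events. The outcome stream is solicited and record-based. The safety stream starts from what a woman chooses to mention. The plan joins them nowhere, so an overdose recorded at a study visit, or a fetal demise found in the chart, need not appear in the adverse-event summary.

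At stake is what the investigators see twice a year in a population that the protocol itself calls vulnerable. If the summary is fed mainly by unprompted reports, a low count cannot be read as reassurance. The estimate of the primary outcome is not affected.

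**Working it through.** No formula in the plan applies and there is no stated figure to reproduce. The check is a side-by-side reading.

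**1. Detection versus handling.** Spontaneous self-report is the only detection source named. Staff verification confirms an event already reported; it does not find an unreported one. The duty to document all adverse events and report them to the investigator governs what happens after an event is known, and it names no further source. The section also says that maternal and infant data come from the electronic record, but it presents this as outcome abstraction and does not tie it to adverse-event detection.

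**2. Each event followed to the report.**

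| Event | How it is collected | Stated route into the AE/SAE summary |
|---|---|---|
| Overdose, reversal agent, overdose admission | Interview at every visit | None |
| Miscarriage, fetal demise | Medical record review | None |
| NICU or nursery admission, infant morbidities, infant emergency visits | Records, interview, staff report, Medicaid and discharge data | None |
| Other maternal hospital use | Cornell questionnaire at three time points | None |
| Maternal death, infant death | Not listed | None |

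No text says which of these count as adverse or serious adverse events.

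**3. Does the SAP close the gap?** No. It describes descriptive summaries and a mixed-model comparison of outcomes between arms. It provides no safety tabulation and no periodic one, so being captured as an outcome does not place an event before the investigators at the semi-annual review.

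**4. Where unprompted reporting is weakest, on the protocol's own facts.**
- Infants are study subjects and cannot report. Custody status is tracked at discharge and at 3 and 6 months, so the plan allows for mothers who no longer have the infant and may not know of an event.
- The recruitment section says that a substantial share of potential participants are under criminal justice supervision at some point. That is a plausible reason not to volunteer an overdose. A direct question at each visit is a better prompt, although still self-report, and record, discharge and Medicaid data do not depend on her answer.
- A woman who has disengaged or died cannot report. Discharge and Medicaid data do not depend on attendance.

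**5. Size.** If a proportion *p* of participants have a listed event and a share *c* of those events is volunteered, the number missed is *N* × *p* × (1 − *c*). The documents give neither *p* nor *c*. The missed share, 1 − *c*, could be anything from 0 to 1, and choosing values would only return the choice.

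**The case against.** The strongest reply is proportionality. The trial is classed as no greater than minimal risk, delivers education, gives no study medication and leaves prenatal and substance-use care unchanged. The IRB form asks for a monitoring plan for research above minimal risk or for NIH-funded or FDA-regulated studies, and the funder written in is PCORI. Passive reporting beside systematic outcome collection is a defensible light plan. This stands as an argument about burden. It does not remove the gap, because the protocol, citing the vulnerability of its population, commits itself to a periodic AE/SAE summary and so needs a detection rule that fits it. Anticipating no serious events from the interventions does not say how an overdose or fetal loss is counted.

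The second reply is that nothing excludes the collected events. Staff verification and the duty to document every adverse event could be read broadly, and the attachments list an AE/SAE listing whose content and sources are not shown. This also stands. A reader might infer that self-report is the sole input and that the summary is bound to under-count, but the documents support only that it may.

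A third reply concerns the remedy. Logging every admission would duplicate outcomes such as NICU admission, and tabulating events by arm twice a year would give investigators in an open cluster trial repeated comparative looks that the plan does not provide for. Both points are sound, and the fix below requires neither.

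**Conclusion.** The concern holds as a gap in ascertainment. The one stated means of detecting adverse events is spontaneous self-report, and no rule links the overdose interview, the fetal-loss abstraction or the infant data to the semi-annual summary. That summary may miss serious events already in the trial's database. The size is unknown. The conclusion rests on the text shown and assumes that the unseen AE/SAE listing does not embody a wider rule.

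Some stronger readings go beyond the documents:
- *The principal investigator monitors alone.* Co-investigators give input and follow adverse events to resolution. What can be said is that no independent monitor is named.
- *Deaths are already abstracted.* Neither maternal nor infant death appears in the data lists.
- *All maternal admissions are abstracted from records.* Only overdose admissions are named explicitly. Other use is covered by the questionnaire.
- *The shortfall differs by arm.* Sessions are led on site in one arm and remotely in the other, but trained site personnel collect visit data in both, and nothing in the documents shows a difference.

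This is an inexpensive improvement that should be made. It does not threaten the primary comparison.

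**What to change.** Amend the Data and Safety Monitoring section as follows:

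1. Adverse and serious adverse events are identified from three sources: the overdose interview at every visit; the record, discharge and Medicaid abstraction already planned; and spontaneous report.
2. A short list of collected events enters the AE/SAE log whether or not they are thought related to the intervention: overdose, admission for overdose, miscarriage or fetal demise, and serious infant morbidity, with that last term defined.
3. Maternal death and infant death are added explicitly, both to the data collection list and to the log.
4. The semi-annual summary reports the totals for these events.

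Items 1, 2 and 4 cost protocol wording and a REDCap flag on fields that already exist. Item 3 needs new fields, because deaths are not now listed. The downside is more log entries for staff to process. If the attached AE/SAE listing already draws on these sources, the change reduces to stating that practice in the protocol.

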#### Future Use and Sharing of Material (e.g., Data/Specimens/Information)

If the material collected for this study will be used by members of the research team or shared with other researchers for future studies, please address the following:

- list the biological specimens and/or information that will be kept
- briefly describe the types, categories and/or purposes of the future research
- describe any risks of the additional use
- describe privacy/confidentiality protections that will be put into place
- describe the period of time specimens/information may be used
- describe procedures for sharing specimens/information with secondary researchers
- describe the process for, and limitations to, withdrawal of specimens/data

n/a

Are you recruiting or expect to enroll **Non-English Speaking Subjects or Subjects from a Foreign Culture?** (does not include short form use for incidentally encountered non-English subjects)

Yes  No

Non-English Speaking Subjects or Subjects from a Foreign Culture

#### Recruitment and Consent:

Describe how information about the study will be communicated to potential subjects appropriate for their culture, and if necessary, how new information about the research may be relayed to subjects during the study.

When recruiting Non-English-speaking subjects, provide a consent document in the subject's primary language. After saving this section, attach both the English and translated consent documents in the "Informed Consent" section.

#### Cultural and Language Consultants:

The PI is required to identify someone who is willing to serve as the cultural consultant to the IRB.

- This person should be familiar with the culture of the subject population and/or be able to verify that translated documents are the equivalent of the English version of documents submitted.

- The consultant should not be involved with the study or have any interest in its IRB approval.
- Please include the name, address, telephone number, and email of the person who agrees to be the cultural consultant for your study.
- ORI staff will facilitate the review process with your consultant. Please do not ask them to review your protocol separately.

For more details, see the IRB Application Instructions on [Research Involving Non-English Speaking Subjects or Subjects from a Foreign Culture](#).

**Local Requirements:**

If you will conduct research at an international location, identify and describe:

- relevant local regulations
- data privacy regulations
- applicable laws
- ethics review requirements for human subject protection

Please provide links or sources where possible. If the project has been or will be reviewed by a local ethics review board, attach a copy in the "Additional Information/Materials" section. You may also consult the current edition of the [International Compilation of Human Research Standards](#)

---

Does your study involve **HIV/AIDS research and/or screening for other reportable diseases (e.g., Hepatitis C, etc...)?**

Yes  No

#### HIV/AIDS Research

If you have questions about what constitutes a reportable disease and/or condition in the state of Kentucky, see ORI's summary sheet: "Reporting Requirements for Diseases and Conditions in Kentucky" [[PDF](#)].

**HIV/AIDS Research:** There are additional IRB requirements for designing and implementing the research and for obtaining informed consent. Describe additional safeguards to minimize risk to subjects in the space provided below.

For additional information, visit the online [IRB Survival Handbook](#) to download a copy of the "Medical IRB's requirements for Protection of Human Subjects in Research Involving HIV Testing" [D65.0000] [[PDF](#)], and visit the [Office for Human Research Protections web site](#) for statements on AIDS research, or contact the Office of Research Integrity at [contact].

#### PI-Sponsored FDA-Regulated Research

Is this an investigator-initiated study that:

- 1) involves testing a Nonsignificant Risk (NSR) Device, or
- 2) is being conducted under an investigator-held Investigational New Drug (IND) or Investigational Device Exemption (IDE)?

Yes  No

#### PI-Sponsored FDA-Regulated Research

If the answer above is yes, then the investigator assumes the regulatory responsibilities of both the investigator and sponsor. The Office of Research Integrity provides a summary list of sponsor IND regulatory requirements for drug trials [[PDF](#)], IDE regulatory requirements for SR device trials [[PDF](#)], and abbreviated regulatory requirements for NSR device trials [[PDF](#)]. For detailed descriptions see [FDA Responsibilities for Device Study Sponsors](#) or [FDA Responsibilities for IND Drug Study Sponsor-Investigators](#).

- Describe the experience/knowledge/training (if any) of the investigator serving as a sponsor (e.g., previously held an IND/IDE); and
- Indicate if any sponsor obligations have been transferred to a commercial sponsor, contract research organization (CRO), contract monitor, or other entity (provide details or attach FDA 1571).

IRB policy requires mandatory training for all investigators who are also FDA-regulated sponsors (see [Sponsor-Investigator FAQs](#)). A sponsor-investigator must complete the applicable Office of Research Integrity web based training, (drug or device) before final IRB approval is granted.

Has the sponsor-investigator completed the mandatory PI-sponsor training prior to this submission?

Yes  No

If the sponsor-investigator has completed equivalent sponsor-investigator training, submit documentation of the content for the IRB's consideration.

[Attachments](#)

**HIPAA****0 unresolved  
comment(s)**

Is HIPAA applicable?  Yes  No

(Visit ORI's [Health Insurance Portability and Accountability Act \(HIPAA\) web page](#) to determine if your research falls under the HIPAA Privacy Regulation.)

If yes, check below all that apply and attach the applicable document(s): [?](#)

- HIPAA De-identification Certification Form
- HIPAA Waiver of Authorization

[Attachments](#)

## STUDY DRUG INFORMATION

0 unresolved  
comment(s)

## The term drug may include:

- FDA approved drugs,
- unapproved use of approved drugs,
- investigational drugs or biologics,
- other compounds or products intended to affect structure or function of the body, and/or
- [complementary and alternative medicine products](#) such as dietary supplements, substances generally recognized as safe (GRAS) when used to diagnose, cure mitigate, treat or prevent disease, or clinical studies of [e-cigarettes](#) examining a potential therapeutic purpose.

## Does this protocol involve a drug including an FDA approved drug; unapproved use of an FDA approved drug; and/or an investigational drug?

 Yes  NoIf yes, complete the questions below. Additional [study drug guidance](#).

## LIST EACH DRUG INVOLVED IN STUDY IN THE SPACE BELOW

Drug Name:

Note: Inpatient studies are required by Hospital Policy to utilize [Investigational Drug Service \(IDS\) pharmacies \(Oncology or Non-Oncology\)](#). Use of IDS is highly recommended, but optional for outpatient studies. Outpatient studies not using IDS services are subject to periodic inspection by the IDS for compliance with drug accountability good clinical practices.

Indicate where study drug(s) will be housed and managed:

 Investigational Drug Service (IDS) UK Hospital

Other Location:

Is the study being conducted under a valid Investigational New Drug (IND) application?

 Yes  No

If Yes, list IND #(s) and complete the following:

IND Submitted/Held by:

Sponsor: Held By: Investigator: Held By: Other: Held By: 

Checkmark if the study is being conducted under FDA's Expanded Access Program (e.g., Treatment IND) or if this is an Individual Patient Expanded Access IND ([FDA Form 3926](#)).

[FDA's Expanded Access Program Information for Individual Patient Expanded Access INDs](#), and attach the following:

- [FDA Form 3926](#);
- FDA expanded access approval or correspondence;
- Confirmation of agreement from manufacturer or entity authorized to provide access to the product.

For guidance and reporting requirements at the conclusion of treatment see the [Expanded Access SOP](#).

Complete and attach the required [Study Drug Form](#) picking "Study Drug Form" for the document type. Any

applicable drug documentation (e.g., Investigator Brochure; approved labeling; publication; FDA correspondence, etc.) should be attached using "Other Drug Documentation" for the document type.

Attachments

## STUDY DEVICE INFORMATION

0 unresolved  
comment(s)

## A DEVICE may be a:

- component, part, accessory;
- assay, reagent, or in-vitro diagnostic device;
- software, digital health, or mobile medical app;
- other instrument if intended to affect the structure or function of the body, diagnose, cure, mitigate, treat or prevent disease; or
- a homemade device developed by an investigator or other non-commercial entity and not approved for marketing by FDA.

For additional information, helpful resources, and definitions, see ORI's [Use of Any Device Being Tested in Research web page](#).

**Does this protocol involve testing (collecting safety or efficacy data) of a medical device including an FDA approved device, unapproved use of an approved device, humanitarian use device, and/or an investigational device?**

Yes  No

[Note: If a marketed device(s) is only being used to elicit or measure a physiologic response or clinical outcome, AND, NO data will be collected on or about the device itself, you may answer "no" above, save and exit this section, (Examples: a chemo drug study uses an MRI to measure tumor growth but does NOT assess how effective the MRI is at making the measurement; an exercise study uses a heart monitor to measure athletic performance but no safety or efficacy information will be collected about the device itself, nor will the data collected be used for comparative purposes against any other similar device).]

If you answered yes above, please complete the following questions.

